##### **12.4.2.2. Serious Adverse Events**

Serious adverse events will be recorded on the AE eCRF and on the SAE eCRF, and health authorities will be notified as outlined in Section [12.5.2](#).

#### **12.5. Recording and Reporting Adverse Events**

After learning that a participant has experienced an AE, the investigator or designee is responsible for recording the AE in the eCRF, regardless of relationship or expectedness. If the AE is determined to be serious, expedited reporting is required per Section [12.5.1](#).

##### **12.5.1. Reporting SAEs to the Sponsor**

The following process for reporting an SAE ensures compliance with 21 CFR 312 and ICH guidelines. After learning that a participant has experienced an SAE, the investigator or designee is responsible for reporting the SAE, regardless of relationship or expectedness, within 1 business day of becoming aware of the event. The initial SAE report should include as much information as possible, but at a minimum must include the following:

- Reporter
- Subject ID
- Serious AE term
- Relationship to study medication(s)

- Reason why the event is serious

Supplemental eCRF pages should be current at the time of SAE reporting: medical history, concomitant medications, demographics, and death as applicable. If an SAE is related or possibly related, unblinding may occur per Section 9.4.

Unavailable details of the event should not delay submission of the known information. As additional details become available, the SAE eCRF should be updated and re-submitted via the EDC system. Every time the SAE eCRF is submitted, it should be signed by the investigator or sub-investigator.

For additional information regarding SAE reporting, contact Rho Product Safety:

Rho Product Safety  
[name]  
[name]  
Toll-free: [name]  
SAE Fax Line: [name]

Email: rho\[contact]

#### **12.5.2. Reporting SAEs to Health Authorities**

The Sponsor will report Investigational New Drug (IND) Safety Reports to the Food and Drug Administration (FDA) and investigators in accordance with the FDA regulations detailed in 21 CFR 312.32.

The sponsor shall promptly review all information relevant to the safety of the drug obtained or otherwise received by the sponsor from any source, foreign or domestic. The sponsor shall notify the FDA and all participating investigators in a written IND safety report of any adverse experience associated with use of the drug that is both serious and unexpected.

These events, which require unblinding, must be reported by the sponsor to the appropriate health authorities within 15 calendar days; fatal or life-threatening events must be reported within 7 calendar days.

#### **12.5.3. Reporting SAEs to IRB(s) or Ethics Committee(s)**

It is the responsibility of the investigators to promptly notify their respective IRB(s) or independent ethics committee(s) (IECs) of IND Safety reports or other matters involving risk to patients as mandated by the IRBs/IECs.

SUSARs are to be reported to the investigators and to the IRBs/IECs when the following conditions occur:

- The event must be an SAE.
- There must be a certain degree of probability that the event is an adverse reaction from the administered drug.
- The adverse reaction must be unexpected, that is to say, not foreseen in the Investigator's Brochure.

#### **12.5.4. Reporting Pregnancy**

During the study, all subjects should be instructed to contact the investigator immediately if they suspect they might be pregnant (e.g., missed or late menstrual period). If pregnancy is confirmed, the subject will be withdrawn from the study and followed until the pregnancy comes to term.

The investigator is responsible for reporting all available pregnancy information within 1 business day of becoming aware of the event. Study treatment must be discontinued immediately in the event of a pregnancy. Monitoring of the participant should continue until the conclusion of the pregnancy. Follow-up information detailing the outcome of the pregnancy should be reported as it becomes available even if the subject was discontinued from the study.

Pregnancy in itself is not regarded as an AE unless there is a suspicion that an investigational product may have interfered with the effectiveness of a contraceptive medication.

Any pregnancy complication or premature terminations including miscarriage, spontaneous abortion, or elective termination of a pregnancy for medical reasons will be reported as an SAE, as described in Section 12.4.2.2. Elective abortions for no medical reason and without complications should not be handled as AEs. Should the pregnancy result in a congenital abnormality or birth defect, a separate SAE report must be submitted. Furthermore, all neonatal deaths that occur within 30 days of the birth should be reported as SAEs, without regard to causality. In addition, any infant death that occurs after the 30-day reporting period that the investigator suspects is related to the *in utero* exposure to the study treatment should also be reported.

### **13. STATISTICS**

Analysis of the clinical efficacy data will consist of modeling endpoints, including PD, CAL, BOP, and FMPI, with treatment group as the main effect and adjusted for baseline. Post-baseline treatment comparisons will be modeled through a generalized estimating equations (GEE) method (with a linear link and exchangeable covariance matrix), adjusting for the baseline value. Methods of analysis for periodontal microbial flora profiles, inflammatory cytokine levels in GCF and in serum and RBL will be described in separate statistical analyses plans. Results will be considered significant if  $p < 0.05$ .

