
Planned Sample Size: The sample size for the study is based on the sample size required to reject the null hypothesis for the primary efficacy endpoint.
 
The number of subjects was estimated based on 2 meta-analysis studies that reviewed 50 and 72 articles respectively (Bonito, 2005) to reach a significant difference in PD reduction at 9 months compared with placebo.
 
Using the normal approximation for sample size determination for 2 independent samples, t-tests, and assuming a PD reduction of 0.5 mm on average (difference in means) with a standard deviation of 0.7 mm, <math>\alpha=0.05</math> (0.025 per comparison), and 85% power, a sample size of 44 per group will be required. The expected dropout rate is 20% based on previous experiments; hence 50 subjects will be enrolled per group. Generalized estimating equations (GEE) analyses will be performed and therefore, the actual power will be between 85 and 90%.

Statistical methods: Analysis of the clinical efficacy data will consist of modeling endpoints, including change from baseline in PD, CAL, BOP, and FMPI, with treatment group as a main effect and adjusting for baseline values of a given endpoint. Post-baseline treatment comparisons will be modeled through a GEE method (with a linear link and exchangeable covariance matrix), adjusting for the baseline value. Methods of analysis for periodontal flora, inflammatory cytokine levels in GCF and in serum, and RBL will be described in separate statistical analysis plans. Results will be considered significant if <math>p < 0.05</math>.

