## 7.2. Number of Subjects

One hundred and fifty (150) subjects will be enrolled. The sample size for the study is based on the sample size required to reject the null hypothesis for the primary efficacy endpoint which contains two comparisons. Using the normal approximation for sample size determination for two independent samples, t-tests, and assuming a PD reduction of 0.5 mm on average (difference in means) with a standard deviation of 0.7 mm,  $\alpha=0.05$  (Bonferroni corrected,  $\alpha$  0.025 per comparison), and 85% power, a sample size of 44 per group will be required. The expected dropout rate is 20% based on previous experiments and current enrollment trends hence 50 subjects will be enrolled per group. GEE analyses will be performed and therefore, the actual power will be between 85 and 90%.

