2.6 Sample Size Determination

One hundred and fifty (150) subjects will be enrolled. The sample size for the study is based on the sample size required to compare treatment with ST266 versus placebo for the primary efficacy endpoint.

The number of subjects was estimated based on two meta-analysis studies that reviewed 50 and 72 articles respectively (Bonito, 2005).

Using the normal approximation for sample size determination for an independent sample t-test, and assuming a PD reduction of 0.5 mm on average (difference in means) with a standard deviation of 0.7 mm, $\alpha=0.05$ (0.025 per comparison, Bonferroni correction), and 85% power, a sample size of 44 per group will be required. The expected dropout rate is approximately 10% based on previous experiments; hence 50 subjects will be enrolled per group.

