Since there are two primary hypotheses, Bonferroni corrections will control for multiplicity with $p < 0.025$ considered significant. Point estimates and 95% confidence intervals will be presented for the treatment group differences in change from baseline at each assessment time point. These analyses will be performed once all the subjects (excluding those withdrawn) have been unblinded and completed their 270-Day Visit.

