8.3.2 Secondary Efficacy Analyses

Additional secondary efficacy analyses will be performed to test the effects of treatment group and their interactions on the secondary endpoints of the change from baseline in CAL and BOP at Day 270. For the CAL analysis, the GEE analyses will be performed with the same statistical model as described in the primary PD efficacy analysis but with the change from baseline in CAL of tooth-sites with baseline PD ≥ 6 mm as the dependent

variable. Separate hypotheses will be performed for testing the treatment effects of group 1 versus group 3 (placebo) and group 2 versus group 3 (placebo). As described above, this model will include the baseline smoker status (smoker or non-smoker) by treatment group interaction. For the secondary efficacy analyses of the BOP change from baseline, ANCOVA will be performed with treatment group as the main effect, and covariates for baseline PD, site, patients, smoker status, and the baseline smoker status (smoker or non-smoker) by treatment group interaction. Point estimates and 95% confidence intervals will be presented for the treatment group differences in CAL and BOP change from baseline at Day 270 and by baseline smoker status.

The CAL and BOP secondary analyses described above will be tested hierarchically in the order of: CAL change from baseline at Day 270, and BOP (presented as a whole mouth average percentage) change from baseline at Day 270. The treatment effects for the CAL or BOP change from baseline at the Day 270 Visit will be compared between Treatment Group 1 and Placebo, and between Treatment Group 2 and Placebo. The alpha will be set at 0.025 to allow for the Bonferroni correction for 2 multiple comparisons for secondary endpoints. Since the smoker status by treatment group interaction is acting as a gatekeeper for further inference testing by smoker status, no additional corrections will be made for multiplicity for any additional analyses of the effects of treatment on CAL and BOP by smoker status. These analyses will be performed once all the subjects (excluding those withdrawn) completed their 270-Day Visit.

All primary and secondary analyses performed on the ITT population will be repeated using the per protocol population.

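### Protocol 13 and the protocol synopsis declare significance at p<0.05 without qualification, while the sample-size texts and the SAP test rules use 0.025 per comparison (minor)

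*Protocol*

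**What the plan says.** **Protocol, decision rule.** Section 13 describes the GEE models for PD, CAL, BOP and FMPI and closes with "Results will be considered significant if $p < 0.05". The statistical-methods paragraph of the synopsis ends the same way ("statistical analysis plans. Results will be considered significant if", then 0.05). Neither place mentions the two comparisons with placebo.

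**Sample size.** The protocol synopsis gives an overall 0.05 with "0.025 per comparison), and 85% power, a sample size of 44 per group will be required". Protocol 7.2 refers to a "primary efficacy endpoint which contains two comparisons", names Bonferroni and uses the same 0.025. SAP 2.6 has "0.025 per comparison, Bonferroni correction), and 85% power, a sample size of 44 per group will be required", and the SAP's own synopsis (section 2) agrees.

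**SAP, decision rules.** SAP 8.3.1 on PD: "Since there are two primary hypotheses, Bonferroni corrections will control for multiplicity", with 0.025 as the threshold. SAP 8.3.2 on CAL and BOP: "The alpha will be set at 0.025 to allow for the Bonferroni correction for 2 multiple comparisons for secondary endpoints". The SAP synopsis carries no p<0.05 sentence.

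**SAP, intervals.** SAP 3 makes 95% two-sided the general convention, and SAP 8.3.1 follows it: "Point estimates and 95% confidence intervals will be presented for the treatment group differences in change from baseline at each assessment time point". No 97.5% interval is planned.

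**Dates.** The protocol is dated 08 September 2017 and SAP version 4.0 is dated 02 October 2017.

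**The concern.** The threshold decides whether a regimen is declared effective. A PD, CAL or BOP comparison with p between 0.025 and 0.05 is significant under the protocol sentence and not significant under the SAP. Protocol 13.1 and 13.2 hand the population-specific analyses and the imputation methods to the SAP, but nothing in the protocol hands over the significance level. A reader checking a claim against the protocol would therefore find a different rule from the one applied.

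The planned intervals add to the confusion. When p lies between the two thresholds, the 95% interval excludes zero although the 0.025 test fails. The report would then show an interval that seems to support a claim the test rejects.

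**Working it through.** **Inputs.** Difference 0.5 mm, SD 0.7 mm, 85% power, 0.025 per comparison, 44 per group (Protocol 7.2, SAP 2.6). Two-sided tests (SAP 3). Two comparisons sharing one placebo arm, allocated 1:1:1 (Protocol 9.4).

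**1. Which level produced 44?** Normal approximation: n = 2·SD²·(z₁₋α/₂ + z₀.₈₅)² / difference², with 2 × 0.49 / 0.25 = 3.92.

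- At 0.025: 3.92 × (2.2414 + 1.0364)² = 42.1, so 43 per group.
- At 0.05: 3.92 × (1.9600 + 1.0364)² = 35.2, so 36 per group.

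With the noncentral t distribution:

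| Two-sided level | n per group | Power |
|---|---|---|
| 0.025 | 43 | 84.6% |
| 0.025 | 44 | 85.5% |
| 0.05 | 36 | 84.8% |
| 0.05 | 37 | 85.8% |

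The stated 44 is the t-test answer at 0.025; the normal approximation that the documents name gives 43. A level of 0.05 gives 37 or 36 and cannot explain 44.

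**2. Family-wise error for the two PD comparisons.** With equal arms of size n, the shared placebo mean contributes variance SD²/n to differences whose variance is 2·SD²/n, so their correlation is 0.5. Family-wise error = 1 − P(|Z₁| ≤ c and |Z₂| ≤ c).

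| Threshold for each | c | Correlation 0.5 | If independent | Bonferroni bound |
|---|---|---|---|---|
| 0.05 (protocol sentence, literally) | 1.960 | 9.1% | 1 − 0.95² = 9.75% | 10% |
| 0.025 (SAP 8.3.1) | 2.241 | 4.65% | 1 − 0.975² = 4.94% | 5% |

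**3. Where the two rules disagree.** For an unadjusted t-test with SD 0.7 mm and 44 per group, the standard error is 0.7 × √(2/44) = 0.149 mm. The smallest significant difference is 1.988 × 0.1492 = 0.297 mm at 0.05 and 2.281 × 0.1492 = 0.340 mm at 0.025, so the rules split for observed differences of about 0.30 to 0.34 mm. The adjusted GEE will give somewhat different limits.

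The chance that one comparison lands between the thresholds is:

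| True difference | 40 per arm | 44 per arm | 50 per arm |
|---|---|---|---|
| 0 mm | 2.5% | 2.5% | 2.5% |
| 0.3 mm | 11.2% | 11.4% | 11.4% |
| 0.5 mm (planned) | 6.8% | 5.7% | 4.2% |

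The 0.3 mm effect and the 40 per arm are illustrative assumptions. SAP 8.3 analyses the ITT population and SAP 8.1.1 imputes values after dropout, so 40 is not the planned analysis number.

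**4. Intervals.** The interval that matches a 0.025 test is 97.5%. Its width relative to 95% is 2.241 / 1.960 = 1.14 (normal), or 2.281 / 1.988 = 1.15 with t at 44 per group. The two 95% intervals jointly cover both true differences with probability 1 − 0.0907 = 90.9%; two 97.5% intervals do so with probability 1 − 0.0465 = 95.4%.

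**The case against.** The strongest reply is that the matter is already settled. Every text that deals specifically with the two PD comparisons uses 0.025, and SAP 8.3.2 carries the same level to CAL and BOP. The SAP postdates the protocol, is more specific, and drops the p<0.05 sentence. The protocol's 0.05 can also be read as the overall level, since the sizing paragraph in the same synopsis gives 0.05 overall and 0.025 per comparison.

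Most of this stands, and it is why the point is minor. What it does not remove is the wording. The protocol sentence is phrased as a rule for results, is not tied to section 7.2, and follows a list that includes CAL, BOP and FMPI. Within the protocol, 0.025 appears only as a sample-size input and never as a decision rule.

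On intervals, the reply is that 95% is an ordinary reporting convention and that SAP 8.3.1 judges significance by the p-value. That also stands. Unadjusted 95% intervals beside a Bonferroni test need a label; they are not an error. Calling for 97.5% intervals in SAP 8.3.1 alone would contradict the convention in SAP 3 and leave the same mismatch for CAL and BOP.

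**Conclusion.** The conflict is real, and the error lies in the protocol wording. The planned sample size and the SAP tests both rest on 0.025 per comparison, and p<0.05 is the outlier. Severity is minor because the operative SAP test is already at 0.025.

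Two stronger readings should be resisted.

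- A reader might infer that the trial runs a 9.1% error rate on its primary endpoint. That would require applying the protocol sentence literally to both comparisons, against Protocol 7.2 and SAP 8.3.1. Under the SAP rule the figure is 4.65%, assuming equal arms and approximately normal test statistics with correlation 0.5; the Bonferroni bound of 5% does not depend on that correlation.
- A reader might infer that the SAP holds 5% across the whole set of primary and secondary tests. The documents do not show this. SAP 8.3.2 orders CAL before BOP, but it does not say that PD must succeed first, and it leaves the by-smoker analyses uncorrected. The 5% statement covers the two PD comparisons only.

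**What to change.** **Protocol 13 and synopsis.** Replace the sentence with: *The overall two-sided significance level is 0.05; each comparison of an active group with placebo (Group 1 vs Group 3, Group 2 vs Group 3) is significant only if two-sided p < 0.025 for PD, and for CAL and BOP as tested in the SAP; p-values for other endpoints are descriptive.*

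**SAP 3**, which governs 8.3.1 and 8.3.2. State that the 95% intervals are not adjusted for multiplicity and that significance is judged by the 0.025 test. Optionally, add 97.5% intervals for the Day 270 PD, CAL and BOP comparisons, written as an explicit exception to the 95% convention in SAP 3.

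**Cost.** One sentence in two places in the protocol and one statement in SAP 3. The sample size, the models and the SAP tests stay as they are. The optional intervals would be about 15% wider than the 95% ones. FMPI would lose the only significance level that the documents give it, so any FMPI p-value would become descriptive, in line with its exploratory status. The change should be made before unblinding, so that the threshold is not chosen with the p-values in view.

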#### **13.1. Analysis Populations**

Statistical analyses will be based on the analysis populations as defined below:

- Safety population: All randomized subjects who use at least one dose of study drug, regardless of whether or not they undergo any study assessments.
- Intention-to-Treat (ITT) population: All randomized subjects.
- Per Protocol (PP) population: All subjects who use at least one dose of study drug and do not deviate from the protocol as per the statistical analysis plan.

Further details regarding the specific analyses associated with each study population are provided in the statistical analysis plan.

#### **13.2. Prevention and Treatment of Missing Data**

Efforts will be made by the sponsor and investigators to maximize subject compliance with the study protocol. Previous studies of adjunctive treatments for periodontitis reported subject completion rates  $>90\%$  (Paquette, 2004). Because this study requires a significant number of in-office treatments, a more conservative estimate of a 20% dropout rate has been made, which is reflected in the sample size calculation (Section 7.2).

Missing data in this study will be treated according to standard practices based on published recommendations of the National Research Council Panel on Handling Missing Data in Clinical Trials (National Research Council, 2010). Methods for imputation of missing data are provided in the statistical analysis plan.

## **14. DIRECT ACCESS TO SOURCE DATA/DOCUMENTS**

### **14.1. Study Monitoring**

Before an investigational site can enter a subject into the study, a representative for the sponsor will visit the investigational study site to:

- Determine the adequacy of the facilities
- Discuss with the investigator(s) and other personnel their responsibilities with regard to protocol adherence, and the responsibilities of Stemnion or its representatives. This will be documented in a Clinical Study Agreement between Stemnion and the investigator.

During the study, a monitor or representative for the sponsor will have regular contacts with the investigational site, for the following:

- Provide information and support to the investigator(s)
- Confirm that facilities remain acceptable
- Confirm that the investigational team is adhering to the protocol, that data are being accurately recorded in the case report forms, and that investigational product accountability checks are being performed
- Perform source data verification. This includes a comparison of the data in the case report forms with the subject's medical records at the clinical site, and other records relevant to the study. This will require direct access to all original records for each subject (e.g., clinic charts).
- Record and report any protocol deviations not previously sent to the sponsor.
- Confirm AEs and SAEs have been properly documented on case report forms, any SAEs have been forwarded to Stemnion and SAEs that met criteria for reporting have been forwarded to the IRB.

The monitor will be available between visits if the investigator(s) or other staff needs information or advice.

### **14.2. Audits and Inspections**

Quality control and quality assurance may be performed before, during, and after the study by the sponsor or authorized personnel. Regulatory authorities in certain countries reserve the right to audit study sites following submission of data in regulatory applications. The investigator may be given due notice of any intended audit by a regulatory body. By signing this protocol and the FDA Form 1572, the investigator acknowledges that these inspection procedures may take place and agrees to provide access to the required subject records and other study documentation. Furthermore, the investigator agrees to inform the sponsor immediately of any known or suspected inspection by authorities. If the investigator does not comply with the protocol, GCP, or regulations, Stemnion, Inc. reserves the right to disqualify the investigator and/or site from the current or future protocols.

